Recent studies of MDD using change from Baseline in MADRS total scores suggest that placebo will yield an approximately nine unit decrease over four weeks with a standard deviation (SD) of around 9.2. SP-624 is expected to yield at least a 12 unit decrease in MADRS total score over four weeks with a similar SD of around 9.2. A minimum of 150 subjects per treatment arm (300 total) would be needed to detect a treatment difference of three units with 80% statistical power. The sample size was estimated using NQuery 8 (V8.5.2.0) two group test of equal means (MTT0-1: www.statsols.com).

Efficacy:

The primary efficacy variable is change from Baseline in MADRS total score at Week 4, for testing superiority of SP-624 vs. placebo. This variable will be analyzed using a Mixed Model for Repeated Measures (MMRM), with change from Baseline in MADRS total score at each visit as the response variable. The MMRM model will include age, weight, and baseline MADRS total score as covariates, with factors for treatment, visit (Weeks 1, 2, 3, and 4; as a categorical variable), treatment by visit interaction term, gender, and site as a fixed effect. An unstructured covariance matrix will be used for the within-subject correlation. Kenward-Rogers approximation will be used to calculate the denominator degrees of freedom. The primary efficacy endpoint will be calculated using an estimate statement. Subjects from low enrolling sites may be pooled in order to help with model convergence.

In the event of a model which fails to converge, analysis strategies will be detailed in the statistical analysis plan (SAP) which will be used to complete the analysis of the primary endpoint. This will include different model assumptions (e.g., restricted maximum likelihood vs maximum likelihood, covariance structure, and removing variables from the model [especially if they are associated with a high degree of missing values]).

Safety:

Laboratory parameters, vital sign data, and ECG results will be summarized by treatment group and presented in tabular and graphic formats where appropriate. Appropriate change from Baseline calculations will be provided to detect any significant changes in laboratory parameters, vital sign values, ECG results, and C-SSRS results, but no formal statistical tests are planned.

Pharmacokinetic Assessments:

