9.3.4.1. Primary Efficacy Endpoint Analysis

The MADRS is a 10-item scale whose total score can range from 0 to 60. The primary efficacy variable is change from Baseline in MADRS total score at Week 4, for testing superiority of SP-624 vs. placebo in adults with major depressive disorder. The analysis will be completed using observed data without imputation. Scores will be taken at 4 weeks regardless of subject discontinuation from treatment. Subjects will not be treated with any other antidepressant medication until at least the completion of the Week 5 visit.

The change from Baseline in MADRS total score at Week 4 will be analyzed from the difference in least square mean change using MMRM, with change from Baseline in MADRS total score at each visit as the response variable. The MMRM model will include age, weight, and baseline

MADRS total score as covariates, with factors for treatment, visit (Weeks 1, 2, 3, and 4; as a categorical variable), treatment by visit interaction term, gender, and site as a fixed effect. An unstructured covariance matrix will be used for the within-subject correlation. Kenward-Rogers approximation will be used to calculate the denominator degrees of freedom. The primary efficacy endpoint will be calculated using an estimate statement. Subjects from low enrolling sites may be pooled in order to help with model convergence.

In the event of a model which fails to converge, additional strategies to address convergence may be required such as alternative covariance structures, using a maximum likelihood versus restricted maximum likelihood (REML) estimation, or dropping variables.

The protocol may include approximately 40 sites and sites with less than 10 subjects will be pooled to obtain at least 10 subjects. Sites would be pooled in order of the site number and, if necessary, the last un-pooled site will be pooled with the last set of sites pooled.

Additional variables of interest that may be evaluated as covariates will be identified in the SAP, such as age of onset of depression and number of lifetime episodes.

Additionally, results from the primary outcome will be summarized for the PP population.

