#### 8 Statistical Methods

#### 8.1 General Reporting Conventions

Study data will be provided in listings and sorted by subject number, study period, and assessment time. The study results will be displayed using descriptive summary tables and inferential analyses completed as described below. Summaries will be displayed by group for all tables and, optionally, for all subjects for baseline tables. For measurements that have multiple intermediate visits, results for observed data will be summarized for each time.

Standard numeric descriptive statistics include number of subjects or records observed (N), mean, standard deviation (std), median, minimum (min), and maximum (max) values. Standard categorical descriptive statistics include the count and percentages of subjects with a level of the variable summarized. Hypothesis tests will assess the null hypothesis that there is no difference in the treatment arms. Two-sided p-values of less than or equal to 0.05 will be considered statistically significant.

All summaries, statistical analyses, and individual subject data listings described below will be completed using Version 9.4 or later of the SAS Statistical Analysis System (SAS Institute, Inc. Cary, NC).

Subjects who are randomized but not treated and those who are treated but have no post-treatment follow-up assessments or data will be listed, but not analyzed. For all listings with dates, the relative study day will be presented, and a minus sign will denote study day is prior to first dose (day 1) while a plus sign will denote number of study days after last dose. Days occurring during treatment period will use neither a plus nor a minus sign.

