#### 8.3.5.4 Primary Efficacy Analysis

The primary efficacy hypothesis will be evaluated by comparing SP-624 to placebo using the mean change from baseline in total MADRS total score after 4 weeks of treatment using a Mixed Model for Repeated Measures (MMRM). The analysis model will include fixed effects for treatment, week and the interaction of week by treatment, and a random effect of subject within treatment. Baseline MADRS total score will be included as a covariate in the model. The treatment difference in terms of the mean change from baseline to a given time point will be estimated and tested from this model. An unstructured covariance matrix will be used to model the correlation among repeated measures. The Kenward-Rogers approximation will be used for the denominator degrees of freedom. The criterion for declaring SP-624 superior to placebo for MADRS total score change from baseline is that the p-value is less than or equal to 0.05.

In the event of a model which fails to converge, the following covariance structures will be considered (in order) until convergence is obtained:

- 1. Heterogenous Toeplitz
- 2. Toeplitz
- 3. First order auto-regressive [AR(1)]
- 4. Compound symmetry

If a covariance structure other than Type=UN is used, a sandwich estimator using the EMPIRICAL option on the PROC MIXED statement will be used.

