#### 8.3.5.5 Sensitivity and Supporting Analyses

A dropout rate of 20-30% is typically seen in MDD studies. Subjects will be grouped by the visit at which they had their last MADRS total score measured. This will result in five categories of discontinuation: Week 1 dropouts, Week 2 dropouts, Week 3 dropouts, Week 4 dropouts, and completers. Mean change from Baseline in MADRS total score will be plotted by the dropout category and by reason for discontinuation, to assess whether this efficacy measure appears to be correlated with study dropout.

The mechanisms that cause missing data may be missing at random (MAR) or may be missing not at random (MNAR). The MMRM model (as implemented within the PROC MIXED procedure in SAS) used in the primary analysis of the primary efficacy endpoint relies on the assumption of MAR.

Therefore, a sensitivity analysis using the tipping-point approach may be used to assess the robustness of the primary analysis approach, in the event the primary analysis is positive. Missing data are first imputed for all visits under the missing-at-random (MAR) assumption, and then a worsening/shift is applied. This is repeated until the result is no longer statistically significant (i.e., p>0.05). The tipping point (smallest worsening/shift in which the significant result turns non-significant) provides a measure of robustness of the primary result. Additionally, in the event the primary analysis is positive a multiple

Form STAT401.V3 Page 13 of 23

Client/Project	Arrivo/Sirtsei 201
Version and Date	V01 August 26, 2022

imputation analysis will be performed with 100 imputations of the study data using available results and variables used in the primary analysis (week, treatment, week to treatment interaction, and baseline MADRS score) to model missing data for each treatment group. Each imputed dataset will be analyzed separately using the same MMRM model in the primary efficacy analysis. The estimates from the imputed model analyses will be combined for statistical inference.

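### The primary MMRM has no baseline-by-week term, so one baseline-MADRS slope serves all four weeks; adding the term is a free, small improvement at Week 4

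*SAP*

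**What the plan says.** SAP 8.3.5.4 specifies the mean model in two statements: "The analysis model will include fixed effects for treatment, week and the interaction of week by treatment, and a random effect of subject within treatment" and then "Baseline MADRS total score will be included as a covariate in the model". The covariance is free: "An unstructured covariance matrix will be used to model the correlation among repeated measures". SAP 8.3.5.5 restates the variables for the multiple imputation as "variables used in the primary analysis (week, treatment, week to treatment interaction, and baseline MADRS score", again with no baseline-by-week term.

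The protocol's model (Synopsis and Section 9.3.4.1) has more covariates but the same feature. It reads "The MMRM model will include age, weight, and baseline MADRS total score as covariates, with factors for treatment, visit", and later "treatment by visit interaction term, gender, and site as a fixed effect". Treatment by visit is its only interaction.

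No other planned analysis clearly relaxes the restriction. SAP 8.3.5.6 adds age, or site and site by treatment, to the same MMRM. Each imputed dataset in 8.3.5.5 is analysed with that MMRM too.

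**The concern.** The endpoint is Week 4 alone, but the baseline adjustment is shared by four weeks. The slope of change on baseline at week t is cov(score at t, baseline) / var(baseline) − 1. It therefore moves if the link between baseline and current score weakens with time. A common slope is then a compromise and need not suit Week 4. The unstructured covariance does not repair this, because the restriction sits in the mean model.

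Two things could be at stake. One is precision, since a wrong slope removes less of the baseline variation. The other is bias through missing data. SAP 8.3.5.5 notes that "A dropout rate of 20-30% is typically seen in MDD studies", and SAP 8.3.5.2 excludes scores taken some days after the last dose from the primary analysis. The model in effect predicts the missing Week 4 scores from earlier weeks and baseline. If it uses the wrong slope, and the baseline scores of those missing differ between arms, the errors do not cancel.

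**Working it through.** **1. The plan's own figure.** SAP 5 gives a difference of 3, SD 9.2 and 80% power; SAP 8.1 sets the test: "Two-sided p-values of less than or equal to 0.05 will be considered statistically significant".

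n per arm = 2(1.96 + 0.8416)² × (9.2/3)² = 2 × 7.849 × 9.404 = 147.6, so 148 (149 with a t-test). At 150 per arm, SE = 9.2 × √(2/150) = 1.062 and power = Φ(3/1.062 − 1.96) = 80.6% (80.4% with t). The stated 150 reproduces. It takes no credit for baseline adjustment and includes no allowance for dropout.

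**2. Assumed inputs.** The documents give only the Week 4 SD of 9.2, so the rest is assumed:
- slope b_t growing in equal steps over Weeks 1 to 4, from −0.10 to −0.40 or from −0.15 to −0.60;
- baseline SD s_B of 3.5 or 5 (entry requires MADRS of at least 27, which narrows the range);
- SDs of change either rising (5.5, 7.2, 8.4, 9.2) or flat at 9.2;
- between-week correlation AR(1) 0.7 or 0.8, or exchangeable 0.6.

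**3. Where the common slope comes from (complete data).** It is c = Σ w_t b_t with w = V⁻¹1 / (1′V⁻¹1), where V is the covariance under the fitted model.

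| | Week 1 weight | Week 4 weight | Week 4 slope error, absolute value of b₄ − c |
|---|---|---|---|
| Rising SDs | 0.80 to 1.05 | −0.06 to 0.18 | 0.25 to 0.44 |
| Flat SDs | 0.18 to 0.41 | 0.26 to 0.47 | 0.14 to 0.22 |

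**4. Precision at Week 4.** Variance ratio = 1 + (b₄ − c)² s_B² / (9.2² − b₄² s_B²).
- Largest loss (rising SDs, exchangeable 0.6, b₄ = −0.6, s_B = 5): c = −0.174 and the slope error is 0.426. The ratio is 1 + (0.1815 × 25)/(84.64 − 9.00) = 1.060. Power is 82.7% with the common slope and 84.8% with week-specific slopes.
- A small loss (flat SDs, AR 0.8, b₄ = −0.4, s_B = 3.5): the slope error is 0.147. The ratio is 1 + (0.0216 × 12.25)/(84.64 − 1.96) = 1.003. Power is 81.4% versus 81.5%.

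The full range is 0.9 to 6.0% (rising) or 0.3 to 1.4% (flat), about 0.1 to 2.1 power points. A chance baseline imbalance of one standard error, s_B√(2/150), shifts the contrast by 0.10 to 0.25 points (rising) or 0.06 to 0.12 (flat).

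**5. Dropout.** An unstructured maximum-likelihood MMRM was fitted with and without baseline by week to simulated data with a true Week 4 difference of −3.0, about 25% dropout, rising SDs and AR 0.8. The large-sample runs used 20,000 per arm:

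| Dropout depends on | Common slope | Week-specific slopes | Gap |
|---|---|---|---|
| nothing (complete data), earlier scores, or baseline equally in both arms | −2.97 to −3.02 | −2.97 to −3.02 | at most about 0.02 |
| baseline in one arm only | −2.59 to −2.86 | −2.99 to −3.05 | 0.19 to 0.40 |
| baseline in opposite directions by arm | −2.36 to −2.69 | −3.00 to −3.11 | 0.32 to 0.65 |

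The complete-data and earlier-scores rows were not run for every steep-slope setting.

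A separate set of simulations took 300 subjects, 18 to 23% missing at Week 4, baseline SD 4.5 to 5.5, and baseline correlation falling from 0.60–0.75 at Week 1 to 0.33–0.35 at Week 4. Opposite-direction dropout pushed the estimate the other way: −3.12, −3.42 and −3.42 with a common slope, against −2.98, −3.04 and −3.05. The gaps are 0.14 to 0.38. With outcome-driven dropout the variance ratios were 1.013, 1.047 and 1.033.

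At 150 per arm (700 runs), the one-arm pattern gave power of 67.9% versus 72.6% (mild slopes, s_B = 3.5) and 65.7% versus 79.7% (steep slopes, s_B = 5), with simulation SE about 1.5 to 2 points. Type I error was 4.4 to 6.4% (common) and 3.9 to 6.4% (week-specific). The steep one-arm null setting was not completed.

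**The case against.** The strongest reply is that a common slope is a legitimate specification. Randomisation makes the expected baseline difference zero, so with complete data the contrast is unbiased whatever slope is used. The common-slope model also still beats the unadjusted 80.6% in every setting above. This stands, and it is why the point is minor.

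Three stronger readings are tempting, and the documents do not support them:
- A reader might infer that the slope is always taken mainly from Week 1. That needs variability to rise over the weeks, which is not documented; with flat SDs, Week 1 has at most 0.41 of the weight.
- A reader might infer that the trial loses precision it was sized for. SAP 5 uses an unadjusted two-group comparison, so what is lost is part of an uncounted gain.
- A reader might infer that 20 to 30% dropout biases the primary result. That figure is an amount of dropout. It says nothing about dropout depending on baseline differently by arm, which the bias requires.

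The multiple imputation in SAP 8.3.5.5 may also help. It models missing data for each treatment group, and if done visit by visit within arm, the baseline relation is free. The wording does not settle this, and the analysis runs only if the primary is positive, so it cannot rescue a missed effect. It is partial mitigation at most.

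**Conclusion.** The omission is real and consistent across both documents: one baseline slope is imposed on Weeks 1 to 4. The harm is conditional. If the slope is constant over the weeks, nothing is wrong. If it varies, the Week 4 contrast is adjusted with the wrong slope, and if variability also rises, that slope comes mainly from Week 1. The expected cost is then about 0.3 to 6% in variance, or 0.1 to 2 power points.

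Bias of about 0.1 to 0.65 points appears only if baseline-related dropout differs by arm. Its direction follows that pattern, so it may shrink or inflate the effect. Nothing in the documents indicates that such a pattern is expected. All sizes rest on assumed slopes, SDs and correlations. The sample size is unaffected, and no clear type I error problem appeared in the settings completed. This is a free improvement, not a flaw that invalidates the primary analysis.

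**What to change.** Before unblinding, add a baseline MADRS-by-week fixed effect to the primary MMRM in SAP 8.3.5.4, and carry it into the variable list for the multiple imputation in 8.3.5.5. Record it in SAP 2.2 as a change from the protocol model, with the reason. The SAP is dated August 2022 and the protocol's estimated last visit was November 2021, so the record should show that the change was made blind to treatment.

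The cost is three parameters (four slopes instead of one), using data already collected. If the slopes are in fact equal, almost nothing is lost.

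The matching term in the secondary MMRMs (SAP 8.3.6) is optional. Its benefit was not quantified, four of those scales have only two post-baseline visits, and the SAP already allows those models to be reduced if they do not converge.

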9.1. Determination of Sample Size

Recent studies of MDD using change from Baseline in MADRS total scores suggest that placebo will yield an approximately nine unit decrease over four weeks with a SD of around 9.2. SP-624 is expected to yield at least a 12 unit decrease in MADRS total score over four weeks with a similar SD of around 9.2. A minimum of 150 subjects per treatment arm (300 total) would be needed to detect a treatment difference of three units with 80% statistical power. The sample size was estimated using NQuery 8 (V8.5.2.0) two group test of equal means (MTT0-1: www.statsols.com).

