# 4 Investigational Plan and Study Design

This is a Phase 2, multicenter, double-blind, randomized, placebo-controlled study of the safety and efficacy of SP-624 in the treatment of adult subjects with MDD as defined by the DSM-5. Following the successful completion of a Screening Phase, subjects will be randomized to one of two treatment groups in a 1:1 ratio and will receive SP-624 or placebo over a treatment period of four weeks (Treatment Group 1: SP-624 20 mg/day; Treatment Group 2: Placebo).

Approximately 300 subjects in a 1:1 ratio (150 per treatment group) will be enrolled into the study. Each subject will complete Screening, Baseline, Treatment, and Follow-up Visits.

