# 5 Sample Size Justification

Recent studies of MDD using change from Baseline in MADRS total scores suggest that placebo will yield an approximately nine unit decrease over four weeks with a standard deviation (SD) of around 9.2. SP-624 is expected to yield at least a 12 unit decrease in MADRS total score over four weeks with a

Form STAT401.V3 Page 5 of 23

Client/Project	Arrivo/Sirtsei 201
Version and Date	V01 August 26, 2022

similar SD of around 9.2. A minimum of 150 subjects per treatment arm (300 total) would be needed to detect a treatment difference of three units with 80% statistical power. The sample size was estimated using NQuery 8 (V8.5.2.0) two group test of equal means (MTT0-1: www.statsols.com).

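### If the unstructured model fails, the fallback can end in constant-variance structures whose sandwich SE leaves the Week 4 difference biased when outcome-related dropout differs between arms

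*SAP*

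**What the plan says.** SAP 8.3.5.4 fits an MMRM to the weekly MADRS changes with treatment, week, their interaction and baseline score. It uses an unstructured covariance matrix with Kenward-Roger degrees of freedom and, in addition, a random effect for subject within treatment. For non-convergence, "the following covariance structures will be considered (in order) until convergence is obtained": heterogeneous Toeplitz, Toeplitz, AR(1), compound symmetry. It then adds: "If a covariance structure other than Type=UN is used, a sandwich estimator using the EMPIRICAL option on the PROC MIXED statement will be used." No degrees-of-freedom method is named for that case.

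SAP 8.3.5.5 says that the primary analysis relies on MAR, and notes: "A dropout rate of 20-30% is typically seen in MDD studies." Its tipping-point and multiple-imputation analyses are both conditional on a positive primary result. Table 8.1 excludes observations more than 3 days after the last dose for subjects who discontinue, so a Week 4 score can be left to the model even when the visit took place.

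Protocol 9.3.4.1 is looser. It mentions other covariance structures, ML instead of REML, or dropping variables, in no stated order.

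**The concern.** Under MAR dropout, the likelihood estimate of the Week 4 mean in effect predicts the missing scores from earlier ones, and the prediction slopes come from the fitted covariance matrix. If the structure is wrong, the slopes are wrong and the mean shifts. Heterogeneous Toeplitz lets the variance differ by visit; the three structures after it do not. If change-score variance grows over the four weeks, they carry too little of a leaver's last score forward.

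The sandwich estimates the sampling variance of whatever estimate the working covariance produces. The report could therefore show a robust-looking standard error around a shifted difference. At stake is the primary result, with either lost power or an overstated effect.

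The same paragraph makes the fallback more likely to be reached. A random subject effect adds one constant to every element of the 4×4 covariance matrix. An unstructured matrix already leaves all 4×5/2 = 10 elements free, so that constant cannot be estimated separately.

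**Working it through.** **1. The planned figure.** Inputs: "placebo will yield an approximately nine unit decrease over four weeks with a SD of around 9.2" (Protocol 9.1), a plan to "detect a treatment difference of three units with 80% statistical power" (SAP 5), "subjects will be randomized to one of two treatment groups in a 1:1 ratio" (SAP 4), and "Two-sided p-values of less than or equal to 0.05 will be considered statistically significant" (SAP 8.1).

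n per arm = 2(1.960 + 0.842)² × 9.2² / 3² = 147.6, so 148 (149 with the t distribution). Power at 150 per arm: 3 / (9.2√(2/150)) = 3/1.062 = 2.824, and Φ(2.824 − 1.960) = 80.6%. The stated 150 is reproduced, and 3 points is the yardstick for any bias.

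**2. Mechanism, by hand.** Assume SDs of 8.3 at Week 3 and 9.2 at Week 4 with correlation 0.82. Using the last score alone, the slope of Week 4 on Week 3 is 0.82 × 9.2/8.3 = 0.91. A constant-variance structure sets the SD ratio to 1, which gives 0.82 even if the correlation is right. For someone leaving after Week 1 with an assumed SD of 5, the true ratio is 9.2/5 = 1.84 and is again set to 1. Poor responders who leave placebo are then predicted too favourably, placebo looks better, and the difference shrinks.

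**3. Large-sample bias.** REML fits with treatment-by-visit means, 400,000 per arm, no baseline covariate. Assumed, because the documents give only SD 9.2 and 20-30% dropout:
- weekly SDs 5/7/8.3/9.2;
- adjacent-visit correlations rising from 0.60 to 0.82, or correlations banded by lag at 0.72/0.58/0.48;
- placebo means −3.5/−6/−7.8/−9;
- about 20-29% dropout per arm.

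The difference is drug minus placebo, so positive bias hides benefit. With placebo dropout driven by poor response and drug dropout unrelated to outcome:

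| Structure | Bias at Week 4 (points) |
|---|---|
| Unstructured | 0.00 |
| Heterogeneous Toeplitz | 0.00 if banded; about +0.27 if not |
| Toeplitz | +0.43 to +0.52 |
| AR(1) | +0.45 to +0.52 |
| Compound symmetry | +0.47 to +0.61 |

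For the constant-variance structures this is 0.43/3 = 14% to 0.61/3 = 20% of the planned effect. Varying the assumptions for those three structures:
- Arms swapped: −0.44 to −0.60, favouring the drug.
- Same dropout rule in both arms: 0.00 with no effect; +0.04 to +0.12 with an effect of 3.
- Poor responders leave placebo and improvers leave drug: +0.86 to +1.24.
- Milder SD rise (7.5 to 9.2), placebo-only mechanism: +0.10 to +0.39.

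With SD constant at 9.2, correlations not banded, the placebo-only mechanism and an effect of 3: unstructured +0.03, heterogeneous Toeplitz +0.40, Toeplitz +0.24, AR(1) +0.37, compound symmetry +0.05.

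**4. What the sandwich does.** 150 per arm, 400 replicates, rising SDs, correlations not banded.
- *Same dropout rule, no effect.* The estimate's true SD is about 1.18 under the constant-variance structures. The model-based SE is 0.91-0.92 (rejection 11-12%) and the sandwich SE is 1.12-1.13 (rejection 6%). The SE is repaired.
- *Placebo-only mechanism, effect 3.* Power with the sandwich is 71% unstructured, 62% heterogeneous Toeplitz, 54% Toeplitz and AR(1), and 50% compound symmetry. Interval coverage falls from 95% (unstructured) to 92% (Toeplitz, AR(1)) and 90% (compound symmetry). The fall from 80% to 71% comes from missing data, not from the fallback. The unstructured fit averaged +0.11 here by chance (Monte Carlo SE 1.20/√400 = 0.06). Relative to it, the shifts are 0.64 − 0.11 = +0.53 for Toeplitz and AR(1), and 0.73 − 0.11 = +0.62 for compound symmetry.
- *Placebo-only mechanism, no effect.* Rejection is 3.5% unstructured, 5% heterogeneous Toeplitz, 6% Toeplitz and AR(1), and 7.5% compound symmetry (Monte Carlo SE about 1 point).

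**5. Alternative structures.** With rising SDs and the placebo-only mechanism, across several assumed correlation patterns: heterogeneous Toeplitz 0.00 to +0.28, ARH(1) +0.13 to +0.40, CSH −0.18 to +0.14.

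**The case against.** The strongest reply is that the constant-variance structures may never be used. They apply only after both the unstructured and heterogeneous Toeplitz fits fail. Four visits and about 300 subjects should support 10 covariance parameters: with no random effect and 10% dropout per interval, the unstructured ML estimate existed in 2000 of 2000 simulated datasets. That stands in part. It shows that a solution exists, but it does not test the optimiser in PROC MIXED or the model as written with its random effect.

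The SAP also has a partial safeguard. After a positive result, multiple imputation completes the data by treatment group, and the analysis covariance then has little influence on the Week 4 difference. A drug-favouring bias that produced a positive result would thus meet a check, although the SAP does not state the imputation model's covariance. A bias that hides an effect meets none in the SAP. Protocol 9.3.5 plans a pattern-mixture analysis whatever the result, but SAP 8.3.5.5 does not carry it over. An ordered list is also tighter than the protocol's wording.

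A reader might infer more than the documents support:
- *That the fallback goes straight to constant variance.* It does not; its first step is heterogeneous.
- *That outcome-dependent dropout alone is enough.* When both arms share the rule, the bias is at most about 0.1. Nothing in the documents says that the arms will differ.
- *That heterogeneous structures cure the problem.* They do not always, and under constant variance they have no such advantage.
- *That the Kenward-Roger mismatch matters numerically.* The critical t is 1.972 at 200 df and 1.968 at 298 df.

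**Conclusion.** The point holds as a conditional weakness in the fallback; the planned unstructured analysis was essentially unbiased under every assumption tried. If Toeplitz, AR(1) or compound symmetry is reached, and outcome-related MAR dropout differs between arms, the sandwich does not protect the Week 4 estimate.

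The size is about 0.4 to 0.6 of 3 points under the steeper assumed SD rise with a placebo-only mechanism, and 0.1 to 0.4 under the milder one. The direction depends on which arm loses its poor responders. Heterogeneous Toeplitz shares the problem, at about +0.3, when correlations are not banded by lag. All these sizes rest on assumed weekly SDs, correlations and dropout rules, and the probability of reaching the fallback is unknown. Any excess of false positives was small in the scenario simulated. The change is still worth making: it protects the primary estimate at almost no cost.

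**What to change.** Amend SAP 8.3.5.4 and 8.3.5.5 as follows:

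1. Delete the random effect of subject within treatment. Step 2 helps only if this is done, because the Cholesky form is the same model and would remain unidentifiable.
2. On non-convergence, first refit the same unstructured model as TYPE=FA0(4), and with other starting values.
3. Only then simplify, to heterogeneous Toeplitz, ARH(1) and CSH, in place of Toeplitz, AR(1) and compound symmetry. State that these reduce the bias when variance rises over visits but do not always remove it.
4. Name a degrees-of-freedom method, such as between-within, for any sandwich analysis instead of Kenward-Roger. This is numerically minor.
5. If any structure other than unstructured is used, also run multiple imputation under an unstructured imputation model, whatever the primary result.

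The cost is SAP wording, a few more covariance parameters, and a little more analysis in a contingency that may not arise.
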